9.4. Definitions

9.4.1. Adverse Event (AE)

An AE is defined as any untoward medical occurrence in a subject or clinical investigation subject administered a pharmaceutical product and which does not necessarily have to have a causal relationship with this treatment. An AE can, therefore, be any unfavorable and unintended sign (including an abnormal laboratory finding, for example), symptom, or disease temporally associated with the use of a medicinal product, whether or not considered related to the medicinal product (ICH E2A Guideline. Clinical Safety Data Management: Definitions and Standards for Expedited Reporting, Oct 1994).

It is the responsibility of Investigators, based on their knowledge and experience, to determine those circumstances or abnormal laboratory findings which should be considered adverse events.

9.4.2. Serious Adverse Event (SAE)

Any untoward medical occurrence that at any dose:

- Results in death,
- Is life-threatening,
- Requires inpatient hospitalization or prolongation of existing hospitalization,
- Results in persistent or significant disability/incapacity,
- Is a congenital anomaly/birth defect, or

- Is an important medical event.

Note: The term “life-threatening” in the definition of “serious” refers to an event in which the subject was at risk of death at the time of the event; it does not refer to an event which hypothetically might have caused death if it were more severe (ICH E2A Guideline. Clinical Safety Data Management: Definitions and Standards for Expedited Reporting, Oct 1994).

Medical and scientific judgment should be exercised in deciding whether expedited reporting is appropriate in other situations, such as important medical events that may not be immediately life-threatening or result in death or hospitalization but may jeopardize the subject or may require intervention to prevent one of the other outcomes listed in the definition above. Examples include allergic bronchospasm, convulsions, and blood dyscrasias or development of drug dependency or drug abuse.

Note:

- A procedure is not an AE or SAE, but the reason for the procedure may be an AE or SAE.
- Pre-planned (prior to signing the ICF) procedures or treatment requiring hospitalizations for pre-existing conditions which do not worsen in severity are not SAEs.

9.4.3. AE Severity

The following definitions should be used to assess intensity of AEs:

- Mild: Awareness of sign or symptom, but easily tolerated (i.e., does not interfere with subject’s usual function).
- Moderate: Discomfort enough to cause interference with usual activity.
- Severe: Incapacitating with inability to work or do usual activity (i.e., interferes significantly with subject’s usual function).

9.4.4. Causality Assessment

The Investigator should assess causal relationship between an AE and the study product on the basis of his/her clinical judgment and the following definitions. The causality assessment should be made based on the available information and can be updated as new information becomes available.

- 1 = Related:
 - The AE follows a reasonable temporal sequence from study drug administration, and cannot be reasonably explained by the subject’s clinical state or other factors (eg, disease under study, concurrent diseases, and concomitant medications).
 - The AE follows a reasonable temporal sequence from study drug administration, and is a known reaction to the drug under study or its chemical group, or is predicted by known pharmacology.

- 2 = Not Related:
 - The AE does not follow a reasonable sequence from study product administration, or can be reasonably explained by the subject's clinical state or other factors (eg, disease under study, concurrent diseases, and concomitant medications).

9.4.5. Action Taken Regarding the Study Product

- 1 = Dose Not Changed: No change in study drug dosage was made.
- 2 = Drug Withdrawn: The study product was permanently stopped.
- 3 = Drug Interrupted: The study product was temporarily stopped.

9.4.6. Adverse Event Outcome

- 1 = Recovered/Resolved
 - The subject fully recovered from the adverse event with no residual effect observed.
- 2 = Recovered/Resolved with Sequelae
 - The residual effects of the adverse event are still present and observable.
 - Include sequelae/residual effects.
- 3 = Not Recovered/Not Resolved
 - The AE itself is still present and observable.
- 4 = Fatal

9.4.7. Other Action Taken for Event

- 1 = None.
 - No treatment was required.
- 2 = Medication required.
 - Prescription and/or OTC medication was required to treat the AE.
- 3 = Other.

9.5. Serious Adverse Event Reporting Procedure For Investigators

All AEs, SAEs, and AESIs will be reported in the eCRF.

The following types of events should be reported in the eCRF within 24 hours of awareness:

- SAEs (see Section [9.4.2](#) for definition)

- Hepatic events meeting combination abnormalities (eg, ALT or AST ≥ 3 x ULN with simultaneous total bilirubin ≥ 2 x ULN) (potential Hy's Law case), both serious and non-serious
- Any event meeting the stopping rules for individual subjects (see Section 3.1.5.1).

All events (serious and non-serious) must be reported with Investigator's assessment of the event's seriousness, severity, and causality to the blinded study drug. A detailed narrative summarizing the course of the event, including its evaluation, treatment, and outcome should be provided. Specific or estimated dates of event onset, treatment, and resolution should be included when available. Medical history, concomitant medications, and laboratory data that are relevant to the event should also be summarized in the narrative. For fatal events, the narrative should state whether an autopsy was or will be performed, and include the results if available. Source documents will be retained in site's files and should not be submitted to the Sponsor for SAE reporting purposes.

Urgent safety queries must be followed up and addressed promptly. Follow-up information and response to non-urgent safety queries should be combined for reporting via the eCRF to provide the most complete data possible within each follow-up.

In the event that the eCRF is unavailable, report SAEs by faxing the paper Serious Adverse Event Report (SAVER) Form to the CRO using the provided fax cover sheet and the appropriate fax number provided for your country. Once the eCRF becomes available, please enter SAEs reported on the SAVER Form into the eCRF as soon as possible. Please refer to the eCRF Completion Guide for additional instructions.

Please call the local SAE Hotline or your study monitor for any questions on SAE reporting.

9.5.1. Notifying Regulatory Authorities, Investigators, and IRB/EC

Daiichi Sankyo and/or CRO will inform Investigators, IRBs (Institutional Review Board)/ECs (Ethics Committees), and regulatory authorities of any Suspected Unexpected Serious Adverse Reactions (SUSARs) occurring in other study centers or other Daiichi Sankyo studies of the investigational product, as appropriate per local reporting requirements.

In the US, upon receipt of the Sponsor's notification of SUSARs that occurred with the investigational product, unless delegated to the Sponsor, it is the Investigator's responsibility to inform the IRB per Sponsor's instruction.

In the European Economic Area states, it is the Sponsor's responsibility to report SUSARs to all ECs.

9.6. Exposure In Utero During Clinical Studies

Daiichi Sankyo must be notified of any subject who becomes pregnant while receiving or within 4 weeks of discontinuing the investigational product.

Although pregnancy is not technically an AE, all pregnancies must be followed to conclusion to determine their outcome. This information is important for both drug

safety and public health concerns. It is the responsibility of the Investigator, or designee, to report any pregnancy in a female subject using the Exposure In Utero (EIU) Reporting form. Please contact your study monitor to receive the EIU Reporting Form upon learning of a pregnancy. The Investigator should make every effort to follow the subject until completion of the pregnancy. If the outcome of the pregnancy meets the criteria for immediate classification as an SAE (i.e., post-partum complications, spontaneous abortion, stillbirth, neonatal death, or congenital anomaly, including that in an aborted fetus), the Investigator should follow the procedures for reporting SAEs outlined in Section 9.5.

9.7. Clinical Laboratory Evaluations

Blood and urine samples for clinical laboratory evaluations will be shipped to a central laboratory for analysis. Results of all clinical laboratory tests will be reported in the subject's eCRF or merged electronically with the clinical database.

9.7.1. Hematology

A single 4 mL EDTA tube of blood will be drawn for the hematology assessments listed in Table 9.1. These will be measured from samples obtained at the visits indicated at the Schedule of Events (Section 17).

Table 9.1: Hematology Analytes

Hemoglobin
Hematocrit
Red blood cell (RBC) count (with indices)
Reticulocyte count
White blood cell (WBC) count (with differential)
Platelet count

9.7.2. Blood Chemistry

An 8.5 mL serum separating tube of blood will be drawn for the blood chemistry assessments listed in Table 9.2. These will be measured from samples obtained at the visits indicated at the Schedule of Events (Section 17).

Table 9.2: Blood Chemistry Analytes

Sodium	Lactate Dehydrogenase
Potassium	Creatinine
Magnesium	Blood urea nitrogen
Bicarbonate	Total protein
Calcium	Albumin
Inorganic phosphorus	Uric acid
AST	Creatine kinase
ALT	Total cholesterol
ALP	Triglycerides
Total bilirubin	

ALP: alkaline phosphatase; ALT: alanine aminotransferase; AST: aspartate aminotransferase;

9.7.2.1. Estimation of Creatinine Clearance

Creatinine clearance will be estimated from serum creatinine by the central laboratory using the Cockcroft-Gault equation.

9.7.3. Urinalysis

Standard urinalysis (Table 9.3), including a microscopic examination, will be conducted for all subjects at the visits indicated at the Schedule of Events (Section 17).

Table 9.3: Urinalysis Determinations

Specific gravity	Blood
pH	RBC
Protein	WBC
Glucose	Bilirubin
Ketones	Urobilinogen

RBC: red blood cell; WBC: white blood cell.

For samples with findings on macroscopic analysis, microscopic examination for RBCs, WBCs, bacteria, and casts should be performed.

9.7.4. Pregnancy Testing

Serum pregnancy testing will be performed for all WOCBP women, at the Screening and End-of-Treatment Visits. Urine pregnancy tests must be confirmed as negative before randomization and dispensing of study medication. If a urine test is positive, a blood sample will be drawn for serum confirmation.

9.8. Vital Signs

Vital signs will be recorded at all clinic visits (except the Baseline Visit) and will include temperature, heart rate, and supine and orthostatic blood pressure.

For measurement of supine blood pressure, subjects should be in a supine or semi-recumbent position for a minimum of 5 minutes before the blood pressure measurement. Measurement of orthostatic blood pressure should follow measurement of supine blood pressure. Subjects should be asked to stand for 3 minutes before measurement of orthostatic blood pressure. Measurement of blood pressure should be conducted using a calibrated sphygmomanometer or automatic inflatable cuff monitor; the blood pressure cuff should be kept in place between supine and orthostatic blood pressure measurements.

Blood pressure should be measured using the same arm and measuring device throughout the study. At the Screening Visit (Visit 1) only, a blood pressure reading should be taken in both arms (unless there is a medical reason not to use a particular arm). The arm with the higher systolic reading should then be used throughout the rest of the study.

Blood pressure should be recorded to the nearest 2 mmHg mark on the manometer or to the nearest whole number on an automatic device.

9.9. Electrocardiograms

A 12-lead ECG will be conducted at the Screening Visit and at the End-of-treatment Visit. ECG recordings should be assessed as normal or abnormal, and any abnormal findings should be assessed as not clinically significant or significant. Clinically significant abnormal findings should be reported as medical history (if pre-existent or as AEs). Refer to Section 9.1 for general guidance on when to report abnormal findings as AEs.

9.10. Physical Findings

9.10.1. Body Height and Weight

Measurement of height will be performed at Screening Visit, with the subject in a standing position and with shoes removed. The subject's knees should be straightened, head held erect, with eyes forward.

Subjects should be weighed on the same scale when possible.

9.10.2. Physical Examinations

A full physical examination, with the exception of pelvis, breast, and rectum in women and the genitourinary system and prostate in men, will be performed at the Screening Visit and End-of-treatment Visit.

The full physical examination should minimally include clinical evaluations of the head, neck, thyroid, eyes, ears, nose, throat, heart, lungs, lymph nodes, abdomen, skin, extremities, and musculoskeletal system.

For a given subject, physical examinations should be performed by the same examiner when possible.

9.10.3. Neurological Examinations

A neurological examination will be performed at the indicated visits in the Schedule of Events (Section 17).

The neurological examination will include the following: Cranial nerve examination (sense of smell (I), visual fields and acuity (II), eye movements (III, IV, VI) and pupils (III, sympathetic and parasympathetic), sensory function of face (V), strength of facial (VII) and shoulder girdle muscles (XI), hearing (VII, VIII), taste (VII, IX, X), pharyngeal movement and reflex (IX, X), tongue movements (XII). Motor system examination includes muscle strength (0 to 5 rating; grip strength, elbow flexion, knee flexion, ankle dorsiflexion), muscle tone and signs of rigidity. Deep tendon reflexes (0 to 4 rating scale; biceps, brachioradialis, knee jerk, ankle jerk, plantar flexion [i.e., Babinski sign]), Sensory system testing by provoking sensations of fine touch, pain and temperature. Cerebellar testing (great toe and index finger, then proximal assessments; level of abnormality recorded), and gait/station (observation of regular walking, heel-to-toe [tandem] walking, each assessed as normal or abnormal).

For a given subject, neurological examinations should be performed by the same examiner when possible.

9.11. Other Safety Assessments

9.11.1. Columbia Suicide Severity Rating Scale

The C-SSRS will be administered by the Investigator or a qualified designee trained in its administration using the study-specific tablet at all the indicated visits in the Schedule of Events (Section 17).

The C-SSRS is a standardized instrument that was developed to assess the severity of and monitor changes in suicidal ideation and behavior.⁹ Four constructs are measured. The first is severity of ideation, rated on a 5-point ordinal scale. The second is intensity of ideation, which comprises 5 items (frequency, duration, controllability, deterrents, and reason for ideation); each rated on a 5-point ordinal scale. The third is behavior, rated on a nominal scale that includes actual, aborted, and interrupted attempts; preparatory behavior; and non-suicidal self-injurious behavior. The fourth is lethality, which assesses actual attempts; actual lethality is rated on a 6-point ordinal scale, and if actual lethality is zero, potential lethality of attempts is rated on a 3-point ordinal scale.

9.11.2. Physician Withdrawal Checklist

The PWC will be administered by the Investigator or designee using the study-specific tablet at the Follow-up Visits 12, 13 and 14. At Follow-up Visits 12 and 14, the PWC will be administered by telephone.

Although developed specifically to measure symptoms of benzodiazepine withdrawal,¹⁰ the PWC also has been used in studies of pregabalin.^{11,12,13} The PWC rates 20 common

symptoms of withdrawal. The symptoms measured are based on those that are potentially related to benzodiazepine withdrawal: somatic, mood, cognitive, fatigue, and gastrointestinal.

Each of the 20 individual items on the PWC is rated as not present, mild, moderate, or severe. Individual items rated as mild, moderate or severe should not be handled as individual TEAEs. Rather, for any subject with at least 1 individual item rated as mild, moderate, or severe, the Investigator should report “withdrawal” as a TEAE.

In addition, the Investigator should be particularly attentive to any potential TEAEs that suggest opiate withdrawal at the Follow-up visits.

10. OTHER ASSESSMENTS

Not applicable.

11. STATISTICAL METHODS

11.1. Analysis Sets

The following analysis sets will be used to summarize the data from this study:

- The Randomized Analysis Set will include all subjects who signed the ICF and were randomized into the study.
- The Safety Analysis Set will include all subjects who received at least 1 dose of study medication.
- The modified Intent-to-treat (mITT) analysis set will include all randomized subjects who received at least 1 dose of study medication.
- The Per-Protocol Analysis Set will include all subjects who were randomized and received at least one dose of study medication, and who were sufficiently compliant with the protocol according to pre-specified criteria, which will be finalized prior to database unblinding.
- The PK Analysis Set will include all subjects who received at least one dose of DS-5565 and had at least one PK concentration measured.

11.2. General Statistical Considerations

The statistical package SAS® (Version 9.2 or higher) will be used to produce all summary tables, figures, and data listings.

Quantitative data will be tabulated with descriptive summary statistics: arithmetic mean, standard deviation (SD), median, minimum and maximum values, and number of observations. For categorical data, frequency tables will be provided.

For variables expressed as a percentage, the denominators for the calculation of percentage will be the number of subjects who had that variable assessed.

A detailed SAP describing the methodology to be used in the final analysis will be prepared before data unblinding. A change in the planned statistical analysis will require a protocol amendment only if it substantively alters the principal features of the protocol. Any deviations from the planned statistical analyses in the protocol will be fully described in the SAP.

11.3. Study Population Data

Demographic characteristics will be summarized for the Randomized Analysis Set according to treatment assignment. Continuous demographic variables (age [calculated from date of birth to the date of first dose], weight, height, and body mass index) for all randomized subjects will be summarized with descriptive statistics. Categorical demographic variables (sex, race, ethnicity, and age group [eg, non-elderly, elderly, very elderly]) will be summarized with frequency counts and corresponding percentages.

Subject disposition will be summarized as the number of subjects screened, the number randomized, and the number and percentage of those who completed treatment or withdrew (with the latter summarized by reason for withdrawal).

Prior and concomitant medications will be summarized by number and percentage of subjects for each World Health Organization (WHO)-Drug preferred base name and Anatomical Therapeutic Chemical category.

11.4. Efficacy Analyses

11.4.1. Primary Efficacy Analyses

Not applicable.

11.4.2. Secondary Efficacy Analyses

For ADPS, change from baseline measured at randomization to Week 13/ET will be summarized by treatment and compared numerically between treatment groups.

For PGIC at Week 13/ET, the proportions of subjects who are “minimally improved or better” (i.e., score ≤ 3) and of subjects who are “much improved or better” (ie, score ≤ 2) will be summarized and compared numerically between treatment groups.

For each efficacy endpoint, between treatments group differences will be summarized within each CKD stratum by calculating 95% confidence intervals.

11.4.3. Exploratory Efficacy Analyses

Not applicable.

11.5. Pharmacokinetic Analyses

PK analyses, summaries, and listings will be generated by dose group using the PK analysis set. Descriptive statistics for plasma concentrations of DS-5565 (sample size, mean, SD, coefficient of variation, standard error of the mean, minimum, maximum, and median) will be calculated at each evaluation time-point.

A population PK model will be developed to quantify the potential impact of demographic covariates on the exposure to DS-5565. For this purpose, data from this study may be pooled with data from other DS-5565 studies and reported separately from the clinical study report.

11.6. Safety Analyses

For safety endpoints, the data from AE assessments, clinical laboratory assessments, physical and neurologic examinations, 12-lead ECGs, vital signs (including weight) assessments, C-SSRS, and PWC evaluation will make up the safety analyses. The Safety Analysis Set will be used for all safety analyses.

The primary objective is the safety and tolerability of DS-5565. Safety data will be summarized by treatment group. Quantitative data will be tabulated with descriptive summary statistics: arithmetic mean, standard deviation (SD), median, minimum and

maximum values, and number of observations. For categorical data, frequency tables will be provided.

11.6.1. Adverse Event Analyses

AEs will be coded using the Medical Dictionary for Regulatory Activities (MedDRA) classification system. A TEAE is defined as an AE that emerges during treatment (having been absent prior to treatment) or worsens relative to the pre-treatment state. The frequency of patients experiencing a specific TEAE will be tabulated by treatment, system organ class, preferred term, seriousness (see Section 9.4.2), worst severity (see Section 9.4.3), and relationship to study drug (see Section 9.4.4). Treatment-emergent AEs of special interest (defined in the SAP) will be summarized separately. In the by-subject analysis, a subject having the same event more than once will be counted only once. Listings of deaths, SAEs, and AEs leading to treatment discontinuation of a subject will be presented.

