3.1.3. Study Endpoints

The primary safety endpoint is the safety and tolerability of renally adjusted doses of DS-5565 versus placebo.

Specific safety endpoints assessed include:

- All treatment-emergent adverse events (TEAEs)
- Change in clinical laboratory evaluations from baseline measured at randomization to Week 13/ET for DS-5565 versus placebo
- Change in neurological examinations from baseline to Week 13/ET for DS-5565 versus placebo
- Change in electrocardiograms from baseline to Week 13/ET for DS-5565 versus placebo
- Change in Columbia-Suicide Severity Rating Scale (C-SSRS) from baseline to Week 13/ET for DS-5565 versus placebo
- Assessment of Physician Withdrawal Checklist (PWC) at follow-up visits.

The secondary efficacy endpoints include:

- Changes in ADPS from baseline measured at randomization to Week 13/ET for DS-5565 versus placebo. Weekly ADPS is based on daily pain scores reported by the subject that best describes the worst pain over the previous 24 hours.
- Proportion of subjects with improvement in overall status at Week 13/ET as assessed by PGIC for DS-5565 versus placebo.

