6.4. Treatment Period

The Treatment period begins with the first dose on the evening of the Randomization visit (Week 0) and concludes with the End of Treatment visit (Week 13, Visit 11), and therefore will be 13 weeks in duration. During the Treatment period, subjects will visit the clinic after 1 week of treatment (Week 1) and every 2 weeks thereafter (Weeks 3, 5, 7, 9, and 11).

- Fasting is not required prior to the visits.
- Subjects should be instructed to bring their electronic diaries and study medication wallets with them to each clinic visit.

Subjects should maintain their regular diary completion and dosing schedule (i.e., should complete their pain diaries upon awakening and take their morning dose before visiting the clinic) prior to the on-treatment visits, except as follows:

- Subjects should not take their morning dose before visiting the clinic on the morning of a PK sampling visit (Visits 5, 6, 8, and 10 [Weeks 1, 3, 7, and 11])

6.4.1. On-treatment Visits (Visit 5, Week 1; Visits 6-10, Weeks 3, 5, 7, 9, & 11)

The following activities and/or assessments will be performed at/during the on-treatment visits:

- Assess for and record AEs
- Record prior and concomitant medications
- Review daily diaries and ensure diary data has been transmitted properly
- Collect study medication wallets and review medication compliance
- Record vital signs (temperature, heart rate, supine and orthostatic blood pressure), and body weight
- Perform neurological assessment
- Collect blood and urine samples for evaluation of standard laboratory safety tests (chemistry, hematology, and urinalysis)
- PK blood sampling. These blood samples will be collected at the following visits: Visits 5, 6, 8, and 10 (Weeks 1, 3, 7, and 11)
- Complete the C-SSRS and evaluate for continued eligibility (see Section 9.3.1).
- Perform a urine pregnancy test on all WOCBP subjects
- Contact IXRS and obtain new study medication wallet number

- Dispense study drug and review dosing instructions. When subjects are assigned a new medication wallet, the first dose taken from the new medication wallet should be the “PM” dose on Day 1.

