9. SAFETY ASSESSMENTS

9.1. Adverse Events

All clinical AEs occurring after the subject signs the ICF and up to 4 weeks after the last dose of study medication (i.e., follow-up period), whether observed by the Investigator or reported by the subject, will be recorded on the AE eCRF page. Medical conditions (including laboratory values/vital signs that are out of range) that were diagnosed or known to exist prior to informed consent will be recorded as part of medical history.

All clinical laboratory, vital sign, or ECG values should be appraised by the Investigator as to clinical significance. Isolated abnormal laboratory results, vital sign findings, or ECG findings should be reported as AEs if they are symptomatic, lead to study drug discontinuation, require corrective treatment, or are otherwise defined as an adverse event of special interest (AESI) [please refer to Section 9.7].

All SAEs are to be reported according to the procedures in Section 9.5. Always report the diagnosis as the AE or SAE term. When a diagnosis is unavailable, report the primary sign or symptom as the AE or SAE term with additional details included in the narrative until the diagnosis becomes available. If the signs and symptoms are distinct and do not suggest a common diagnosis, report them as individual entries of AE or SAE. For events that are serious due to hospitalization, the reason for hospitalization must be reported as the SAE (diagnosis or symptom requiring hospitalization). A procedure is not an AE or SAE, but the reason for the procedure may be an AE or SAE. Pre-planned (prior to signing the ICF) procedure or treatment requiring hospitalization for pre-existing conditions, which do not worsen in severity, should not be reported as SAEs (see Section 9.4.2 for Definitions). For deaths, the underlying or immediate cause of death should always be reported as an SAE. In addition, any serious, untoward event that may occur subsequent to the reporting period that the Investigator assesses as related to study drug should also be reported and managed as an SAE.

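### The TEAE definition gives no post-dose window: read literally, new non-serious AEs in the 4-week follow-up enter no AE table, in conflict with the instruction to report withdrawal as a TEAE

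*Combined protocol and SAP*

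**What the plan says.** Section 3.1.3 opens its list of specific safety endpoints with "All treatment-emergent adverse events (TEAEs" and closes it with "Assessment of Physician Withdrawal Checklist (PWC) at follow-up visits".

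Section 11.6.1 gives the only TEAE definition: "A TEAE is defined as an AE that emerges during treatment (having been absent prior to treatment) or worsens relative to the pre-treatment state". It then sets out the tables: "The frequency of patients experiencing a specific TEAE will be tabulated by treatment, system organ class, preferred term, seriousness", followed by worst severity and relationship to study drug. AEs of special interest are summarized only if treatment-emergent. The other AE output is: "Listings of deaths, SAEs, and AEs leading to treatment discontinuation of a subject will be presented". No table of all AEs, and no table of post-treatment AEs, is planned.

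Two sections fix the time frame. The Treatment period "concludes with the End of Treatment visit (Week 13, Visit 11" (Section 6.4), and Section 6.5 labels what comes next as post-treatment. AEs are recorded from consent "up to 4 weeks after the last dose of study medication (i.e., follow-up period" (Section 9.1), and they are assessed at Visits 12, 13 and 14.

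Section 9.11.2 has the investigator report withdrawal as a TEAE whenever any checklist item at those visits is rated mild or worse. It adds that "the Investigator should be particularly attentive to any potential TEAEs that suggest opiate withdrawal at the Follow-up visits".

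**The concern.** Safety and tolerability is the primary objective and its analysis is descriptive, so the AE tables are themselves a main result. The rule deciding which AEs enter them has no stated end, and its literal wording disagrees with another section.

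Two things are at stake. First, AEs collected in follow-up may be left out of the tables, or included, according to how the definition is programmed. Second, the events at the center of the conflict are withdrawal-type events. Section 1.3 names abrupt or rapid discontinuation among the cautions for approved drugs of the class and says that these risks are unknown in chronic kidney disease. A reader of the report would expect such events in the AE tables with their coding, severity and causality.

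**Working it through.** **1. The plan's own figure.** Section 11.11: 60 randomized with 25% dropout gives 60 × (1 − 0.25) = 45 completers, as stated. About 60 − 45 = 15 subjects stop early. The point does not depend on this, but it shows how many subjects would have a shorter treatment period before follow-up.

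**2. The definition applied to events after the last dose.**

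| Event after last dose | TEAE on a literal reading of 11.6.1? | Other planned output |
|---|---|---|
| New, non-serious, not captured by another instrument (for example, peripheral edema) | No: it did not emerge during treatment | None named |
| Pre-existing condition that becomes worse | Yes: the worsening limb has no end date | AE tables |
| Withdrawal, from checklist items at Visits 12 to 14 | No under 11.6.1; yes under 9.11.2 | Checklist summary (11.6.8) |
| New laboratory abnormality at Visit 13 | No | Laboratory summary and abnormal-value listing (11.6.2) |
| New finding on vital signs or C-SSRS at Visit 13 | No | Own summaries (11.6.3, 11.6.7) |
| SAE or death | No, if new | Listing (11.6.1) |

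The first row has no planned AE output. The second row shows an inconsistency within the definition: in the same follow-up week, a worsened old headache counts and a new headache does not. The third row is the direct conflict between sections. A first transaminase rise at Visit 13 would be in the laboratory summary but not in the summary of AEs of special interest.

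**3. Early stoppers.** Section 6.4 ends treatment at the Week 13 visit and does not say when it ends for a subject who stops early. Under Section 4.2.1 a subject can miss more than 7 consecutive days of doses and then have the early termination visit. An AE in that gap could be classed either way.

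**4. Share of collection time.** With T weeks on treatment and F = 4 weeks of follow-up, the share is F/(T + F).

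- Completer: 4/(13 + 4) = 4/17 = 23.5%.
- Stop at Week 3 (assumed): 4/(3 + 4) = 57%.
- All 60 subjects, the 15 dropouts leaving on average at Week 12 (assumed): 240/(45 × 13 + 15 × 12 + 240) = 240/1005 = 24%.
- The same, leaving at Week 1 (assumed): 240/(585 + 15 + 240) = 240/840 = 29%.

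The last two lines assume that everyone completes follow-up. All four are shares of time, not of lost events.

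**5. Number of subjects, illustration only.** The documents give no post-treatment AE rate. With 2:1 allocation there are about 40 subjects on DS-5565 and 20 on placebo. If 2% to 20% of subjects (assumed, the same in both arms) had a new non-serious AE only in follow-up, 0.8 to 8 subjects on DS-5565 and 0.4 to 4 on placebo would be affected.

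**The case against.** The strongest case on the other side is that Section 11.6.1 states no cut-off at all. The cut-off appears only when it is joined to Section 6.4, to which it does not refer. Section 9.11.2 shows that the authors use the term TEAE for events at follow-up visits, and Section 11.2 promises a detailed SAP that could set the window. This stands in part: the window is undefined rather than expressly closed. But a literal reading excludes new follow-up events, Section 9.11.2 speaks only of withdrawal-type events, and Section 11.6.1 leaves to the SAP only the definition of AEs of special interest.

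A reader might infer that everything non-serious in follow-up vanishes from the report. The documents do not support that. The checklist at follow-up is a named safety endpoint with its own summary, and laboratory, vital-sign and C-SSRS data from Visit 13 are summarized. Potential Hy's Law cases are reported within 24 hours, and hepatic events go to adjudication.

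A reader might also infer that the safety comparison is biased toward no difference. That is not established. Background late AEs occur in both arms, no post-treatment rates are given, and no test is planned. Only true discontinuation effects would be confined to DS-5565, and the checklist already captures much of what is expected there.

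Finally, 4 weeks reaches well beyond exposure. Section 1.1.5 gives a half-life of 4 to 7 h, and Table 3.1 gives median clearance of 20.0 L/hr in normal function and 4.73 L/hr at CrCl 15-29, a ratio of 4.23. If volume is unchanged (assumed), half-life is about 17 to 30 h, and five half-lives last about 3.5 to 6 days. This is a fair argument against pooling the whole follow-up with on-treatment events. It is not an argument against tabulating it separately.

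**Conclusion.** The concern holds in a limited form. The end of the TEAE window is undefined, its literal reading leaves new non-serious follow-up AEs out of every AE table, and that reading conflicts with Section 9.11.2. What can be lost is other new non-serious follow-up AEs, together with the AE coding, severity and causality of withdrawal-type events.

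The size of the loss cannot be computed from the documents. The only firm figure is that follow-up makes up 4 of 17 weeks of AE collection after first dose for a completer. The conclusion assumes that the definition is applied as written and that treatment ends where Section 6.4 says. The detailed SAP is not among the documents and may already settle the matter; in the text available it is open. Because the conflict concerns the first listed safety endpoint, it should be resolved before unblinding.

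**What to change.** In Section 11.6.1, and in the SAP, state that AEs starting or worsening from first dose to 4 weeks after last dose are tabulated by treatment group, matching the Section 9.1 collection window. Show on-treatment events (first to last dose) and post-treatment events (after last dose to 4 weeks) in separate columns. Anchoring both to dose dates also settles the gap before an early termination visit. Then reword the TEAE definition so that it agrees with Section 9.11.2 on withdrawal at Visits 12 to 14, and apply the same window to AEs of special interest.

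The cost is a short text change and one extra column per AE table. No new data are needed, and sample size is unaffected. Reported AE counts may rise slightly, but the on-treatment column keeps the narrower count visible for anyone who prefers a shorter window.
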